The sample consisted of 36 women and 13 men, divided into two age groups: young people between 18 and 30 years old ($22,438 \pm 3,898$) and adults between 31 and 64 years old ($50,212 \pm 9,633$). In terms of origin, 23 were residents of Plasencia (Spain) and 26 in Castelo Branco (Portugal). The descriptive characteristics of the sample are detailed in Table 1.

Table 1. Descriptive characteristics of the sample.

VARIABLES	Total n=49	Origin	Young Men (mean±SD)	Adult Men (mean±SD)	Young Women (mean±SD)	Adult women (mean±SD)
AGE (years)	41,143± 15,485	Spain Portugal	20±2,828 26±NP	46,333±13.317 46,857±10,495	24,111±3,723 19±2	49±9,367 53.50±8.609
	70,545± 12,705	Spain Portugal	80±14,142 69±NP	87,333±17,926 80,714±11,572	68,667±13,684 66,750±8,995	64,411±7,193 66.857±11.016
HEIGHT (m)	1,664±0 ,085	Spain Portugal	1.82±0.113 1.7±NP	1.733±0.025 1.757±0.060	1,652±0.074 1.657±0.049	1.618±0.068 1,616±0.057
	25,404± 3,626	Spain Portugal	24,026±1,280 23,875±np	29,170±6,725 26,148±3,488	25,069±4,334 24,372±3,837	24,611±2,350 25,552±3,548

n: sample size; SD, standard deviation; NP: Not applicable; kg: kilogram; M: Metro; BMI, body mass index; m^2 : Square meter.

Randomization, masking, and experimental design

Participants were randomly assigned to distinct groups using free software Epidat 4.0 (2011, Galicia, Spain). The blinding was double-blind, so that neither the investigators nor the participants knew the group assigned to the participant until the completion of the study and statistical analysis.

The total number of participants was divided into three groups: a control group (T0) (n=12), in which no participants had a skin infection, and two different treatment groups (T1 and T2) (n=37), with diverse levels of EC. The rest of the participants were included in these two treatment groups, including both infected (n=32) and healthy (n=5) participants. Thus, group T1 (n=25) had 23 participants with infection and 2 healthy participants, and group T2 (n=12) had 9 participants with infection and 3 healthy participants.

The clinical evaluation of the participants was carried out before the start of treatment and, subsequently, on days 15, 30, 45 and 60 of treatment, except for cultures, both mycological and bacterial, which were performed at baseline, at 30 days and at 60 days of treatment. All reviews, sampling, and data collected were performed by the same observer.

Choice of EO, base cream, and preparation of treatments

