A skin sample was taken following the standard procedure described for the diagnosis of mycosis (5). The epithelial surface was disinfected with 70° alcohol and a sample was collected from the affected area by scalpel scraping. Subsequently, the sample was analyzed using two different procedures. The 30% KOH test (35.3g/100ml distilled water) (Labbox, Barcelona, Spain) followed by conventional light microscopy observation to identify the infective fungal agent, and microbiological culture on Sabouraud dextrose agar with chloramphenicol and cycloheximide (Condalab, Torrejón de Ardoz, Madrid), at a constant temperature (between 25°C and 28°C) for 2 to 4 weeks, in order to inhibit molds and bacteria and observe the growth of the infective fungal agent. Participants with infection were considered to be those who had positive results in both tests, excluding cases in which only one test was positive.

- Bacteriological culture

A skin sample was taken following the standardized procedure for microbiological analysis (6). The skin was disinfected with 70° alcohol and a sample was taken by smear with a sterile swab from the affected surface. Again, the analysis was carried out using two distinct and independent procedures. A Gram stain was performed to identify bacteria and the sample was inoculated with Sabouraud dextrose broth (SDA) (Merck, Germany), at a constant temperature (between 27°C and 31°C) for 1 to 3 days. Participants with infection were considered to be those who had positive results in both tests, excluding cases in which only one test was positive.

Variables and statistical analysis

The following variables were analyzed: sociodemographic (sex and age), anthropometric (weight, height, and BMI), hygiene-related habits (frequency of foot washing, use of flip-flops in showers/pools, type of footwear and socks and frequency of sock change), presence or absence and type of infection, degree of hydration and concentration of EC group T0 (0%), group T1 (1%) and group T2 (0.5%). Of these variables, age, weight, height, BMI, and hydration were considered quantitative compared to the rest that were analyzed as qualitative.

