The determination of the specific composition of the 3 types of EO made it possible to quantify the exact concentration of the different components of each of the EO, choosing the EO with the highest concentration of components with antimicrobial activity and the lowest concentration of components susceptible to interaction with other drugs or to produce allergies in the participant, such as terpinolene, alpha-terpinene and sabinene and the aged components of EO(7-10). Specifically, the main component in the 3 EO samples was terpinen-4-ol, with a concentration between 28.47% and 29.15%, followed by gamma-terpinene and alpha-terpinene (Table 2). These three components accounted for approximately 65% of the total EO in the 3 samples analyzed. On the other hand, alpha-terpineol and eucalyptol were found to be the fourth and fifth most concentrated components, with percentages between 3.85%-5.85% and 4.12%-5.81%, respectively. These two, along with m-cymene, alpha-pinene, and terpinolene, made up about 24% of the total EO. The rest of the EO was made up of up to 22 different compounds with minority percentages, considered together as traces. For all the above results, the EO of *M. alternifolia* of the brand Esencias Lozano® was used, since it was the EO that presented the highest percentage of the components of terpinen-4-ol, eucalyptol and alpha-terpineol, whose antimicrobial activity has been described in the bibliography(7,11-14).

Table 2. Percentages of the different components according to the EO studied in the CG-MS.

Components	Trademarks of EO		
	Naissance®	Marnys®	Esencias Lozano®
Terpinen-4-ol	28.47%	29.10%	29.15%
Gamma-terpinene	21.92%	20.42%	22.86%
Alpha-Terpinene	13.10%	11.23%	13.58%
Alpha-terpineol	3.85%	4.03%	5.85%
Eucalyptol	4.12%	4.82%	5.81%
M-cymene	3.40%	5.28%	4.96%
Alpha-pinene	3.18%	3.15%	5.12%
Terpinolene	4.65%	4.26%	3.72%
Traces	17.31%	17.71%	8.95%
Total	100%	100%	100%

®: trademark; %: percentage of the component in the sample.

Test results for microbiological diagnostics

After reading the tests performed for microbiological diagnosis, it was determined that, of the 49 total participants, 32 (65.3%) were positive for skin infections. Of these 32 participants, 4 (12.5%) had fungal infection, 19 (59.4%) showed bacterial infection, and 9 (28.1%) had mixed fungal and bacterial infections simultaneously.

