Of the participants who developed skin infections, 23 were women and 9 were men. The prevalence of skin infections by sex is shown in Table 3.

Table 3. Prevalence of infections as a function of sex.

Sex	Infections			Total
	Fungal	Bacterial	Mixed	
Women	3 (9.3%)	13 (40.6%)	7 (21.8%)	23 (71.7%)
Men	1 (3.1%)	6 (18.8%)	2 (6.4%)	9 (28.3%)
Total	4 (12.4%)	19 (59.4%)	9 (28.2%)	32 (100%)

%: Percentage.

The colorations observed with Wood's light in the interdigital spaces were coral red and opaque blue (Figure 3). The coral-red coloration corresponds to a superficial bacterial infection of the skin caused by *C. minutissimum*, known as erythrasma, and the dull blue coloration corresponds to a fungal infection caused by the dermatophyte *Trichophyton schoenleinii*.

[figure not shown]

Figure 3. Fluorescence of different color emitted by pathogens under Wood's light in interdigital spaces of the feet. (A and B) erythrasma with coral-red coloration (*) and (B) suspected *Trichophyton schoenleinii* with bluish coloration (↑).

Mycological cultures were used to determine the causative agents of fungal infections. The dermatophytes and yeasts that were identified were: *Trichophyton schoenleinii*, *Trichophyton verrucosum*, *Trichophyton tonsurans* and *Candida albicans*. On the other hand, the following bacteria were identified in bacterial cultures: *Corinebacterium minutissimum*, *staphylococcus haemolyticus*, *staphylococcus epidermidis*, *staphylococcus lugdunensis*, *micrococcus luteus* and *micrococcus sp.*

Efficacy of treatments

To test whether the EC-enriched cream was effective against fungal infections, the cumulative survival curves of the two treatments, T1 and T2, were plotted (Figure 4). 100% of fungal infections resolved within 30 days with both treatments, although the EC curve at 1% was higher than 0.5%.

[figure not shown]

Figure 4. Cumulative survival curves as a function of the two treatments for fungal infections.

In fact, the mean time to achieve remission in the T1 group (1%) was 11.61 days, compared to 14.00 days in the T2 group (Table 4). However, according to the Log-rank test, the differences between the two groups were not statistically significant (p -value=0.611). Therefore, both concentrations have similar efficacy in terms of the time required to achieve remission of infection.

Table 4. Mean and median survival time (in days) of remission of fungal infection for the two EC concentrations.

Group	Media				Median			

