	East.	Err. East	IC 95%		East.	Err. East	IC 95%	
			Lim. Inf.	Lim. Sup.			Lim. Inf.	Lim. Sup.
Treatment 1%	11.61	2.68	6.36	16.86	-	-	-	-
Treatment 0.5%	14.00	4.04	6.09	21.91	-	-	-	-

Est: statistical survival test; Err. Est: statistician error; CI, confidence interval; Lim. Inf: lower bound; Lim. Sup: upper limit; "-": data not available.

Similarly, to evaluate whether the EO-enriched cream was effective against bacterial infections, the cumulative survival curves for both treatments were plotted (Figure 5). In this case, the treatment curve at 0.5% concentration showed better results than the 1% treatment curve.

[figure not shown]

Figure 5. Cumulative survival curves as a function of the two treatments for bacterial infections.

Thus, the mean time to achieve remission in the T1 group (1%) was 49.35 days, compared to 44.82 days in the T2 group (0.5%) (Table 5). This indicated that the treatment of the T2 group was better, since the infection remitted 5 days earlier on average, although when comparing both treatments using the Long-rank test, no statistically significant differences were found (p -value=0.130). Median survival was 60.00 days for treatment at 0.5%, so half of the participants in the T2 group achieved remission at the end of the study. This value could not be computed for the 1% treatment, indicating that less than half of the subjects in this group experienced resolution of the infection at the end of the trial (Table 5).

Table 5. Mean and mediansurvival time (in days) of remission of bacterial infection for the two EC concentrations.

Group	Media				Median			
	East.	Err. east.	IC 95%		East.	Err. east.	IC 95%	
			Lim. Inf.	Lim. Sup.			Lim. Inf.	Lim. Sup.
Treatment 1%	49.35	2.38	44.68	54.01	-	-	-	-
Treatment 0.5%	44.82	4.38	36.2	53.40	60.0	6.37	47.51	72.49

Est: statistical survival test; Err. Est: statistician error; CI, confidence interval; Lim. Inf: lower bound; Lim. Sup: upper limit; "-": data not available.

Relationship between infections and the rest of the variables analyzed

In relation to hygiene habits, it was found that most of the participants washed their feet daily, used flip-flops in swimming pools or showers, wore breathable footwear and cotton socks, and changed their socks daily (Table 6), although it is true that these habits did not show a statistically significant relationship with respect to the presence or absence of skin infections ($p\text{-value} \geq 0.103$) (Table 7).

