15. Have you had any of these symptoms on your feet before?

Select all that apply.

- Itching between the toes
- Itching on the bottom of the foot
- Generalized itching of the foot
- Stinging between the toes
- Stinging of the sole of the foot
- Generalized stinging of the foot
- Burning between the toes
- Burning of the sole of the foot
- Widespread burn on the foot
- None of the above

16. Do you have any of these symptoms on your feet today?

Select all that apply.

- Itching between the toes
- Itching on the bottom of the foot
- Generalized itching of the foot
- Stinging between the toes
- Stinging of the sole of the foot
- Generalized stinging of the foot
- Burning between the toes
- Burning of the sole of the foot
- Widespread burn on the foot
- None of the above

17. Have you been diagnosed with fungal infections on your feet before?

Mark only one oval.

- Yes
- No

18. Have you used drug treatment to treat fungal infections in your feet?

Mark only one oval.

- Yes
- No

19. If your previous answers were "YES", could you please tell us what treatment it was?

20. Have you ever been examined by a podiatrist?

Mark only one oval.

- Yes
- No

21. Have you ever had a mycological foot culture?

Mark only one oval.

Yes

No

22. If the previous answer was "YES", please indicate why

23. How often do you wash your feet?

Mark only one oval.

Daily

2 times a day

Less

24. How often do you examine your feet?

Mark only one oval.

Daily

2 times a day

Less

25. What kind of sock do you wear?

Mark only one oval.

Cotton

Polyester

Don't know

26. How often do you change your socks?

Mark only one oval.

Daily

2 times a day

Less

27. Do you wear breathable shoes?

Mark only one oval.

Yes

No

28. What kind of footwear do you usually wear on a daily basis?

Mark only one oval.

Sneakers

Boots/Trekking Boot/ Work/Protective Boots

Other Style

29. How many times a day do you change your shoes?

Mark only one oval.

I usually wear the same shoes all day

I change shoes 2 times a day

I change my shoes according to the activity

I go every day with the same shoes

30. Do you play any sports? If yes, tell us which one and if you don't practice sport, put "NO"

31. If you play a sport, do you usually have specific shoes just for it?

Mark only one oval.

Yes

No

32. Do you wear protection (flip flops) when using showers in gyms, spas, clubs Sports?

Mark only one oval.

Yes

No

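### Table 6 counts 8 fungal and 20 bacterial infections, but the diagnoses give 13 and 28, so the hygiene conclusion rests on counts that contradict the trial's own data

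*Combined protocol and SAP*

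**What the plan says.** Under Test results for microbiological diagnostics, "of the 49 total participants, 32 (65.3%) were positive for skin infections", and the breakdown is "Of these 32 participants, 4 (12.5%) had fungal infection, 19 (59.4%) showed bacterial infection, and 9 (28.1%) had mixed fungal and bacterial infections simultaneously". Table 3 repeats that breakdown by sex, and its lead-in agrees on the total: "Of the participants who developed skin infections, 23 were women and 9 were men".

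The section on randomization, masking and experimental design gives the same total by another route. The treated groups are described as "including both infected (n=32) and healthy (n=5) participants", and there was "a control group (T0) (n=12), in which no participants had a skin infection".

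The diagnostic section applies one rule to both the mycological and the bacteriological work-up: "Participants with infection were considered to be those who had positive results in both tests".

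Table 6 sets five hygiene habits against fungal and bacterial infection in all 49 participants. Each block totals 8 Yes / 41 No for fungal and 20 Yes / 29 No for bacterial infection. Table 7 reports the chi-square tests, and the text concludes that "these habits did not show a statistically significant relationship with respect to the presence or absence of skin infections", with a smallest p-value of 0.103.

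**The concern.** Infection status is the basic classification in this trial, and the report gives two versions of it for the same 49 people. If Table 6 is wrong, the ten tests in Table 7 compared the wrong participants. If the diagnostic breakdown is wrong, Table 3 and the text before it need correcting.

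What is directly at stake is a secondary statement, that hygiene habits are unrelated to infection. There is also a knock-on question. Infection status decides who can enter the remission analyses, and Tables 4 and 5 give no numbers of participants. A reader cannot tell which set of counts was used there.

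**Working it through.** **1. Totals from each source**

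| Source | Any fungal | Any bacterial | Infected | Free of both |
|---|---|---|---|---|
| Diagnostic text and Table 3 | 4 + 9 = 13 | 19 + 9 = 28 | 4 + 19 + 9 = 32 | 49 − 32 = 17 |
| Group description | not given | not given | 23 (T1) + 9 (T2) = 32 | 12 + 5 = 17 |
| Table 6 | 8 | 20 | 20 to 28 | 21 to 29 |

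The Table 6 range follows from the two columns. With complete overlap there are 20 distinct infected people, and with no overlap 8 + 20 = 28. Even the upper limit is 32 − 28 = 4 short. The shortfall by type is 13 − 8 = 5 fungal and 28 − 20 = 8 bacterial.

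**2. Can the handling of the nine mixed cases explain it?** Fungal/bacterial totals would be 13/28 if they count in both columns, 4/19 in neither, 13/19 in fungal only and 4/28 in bacterial only. Splitting them between the columns cannot work either: it would still leave at least 19 + 4 = 23 infections in total across the columns but would cover all 32 people, and 8 + 20 = 28 cannot cover 32.

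**3. Was 8/20 what was actually tested?** I recomputed Table 7 from Table 6 by Pearson chi-square, with continuity correction for the 2×2 tables.

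| Habit | Fungal: printed χ², p | Recomputed | Bacterial: printed χ², p | Recomputed |
|---|---|---|---|---|
| Foot washing | 1.87, 0.393 | 1.87, 0.393 | 1.68, 0.432 | 1.68, 0.432 |
| Flip-flops | 0.00, 0.976 | 0.00, 0.976 | 2.66, 0.103 | 2.66, 0.103 |
| Footwear | 0.00, 1.000 | 0.00, 1.000 | 0.09, 0.761 | 0.09, 0.761 |
| Sock type | 2.64, 0.267 | 2.64, 0.267 | 0.58, 0.748 | 0.58, 0.748 |
| Sock change | 2.15, 0.542 | 2.15, 0.341 | 4.08, 0.252 | 3.88, 0.144 |

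Eight of ten match, so the 8/20 classification is what was analysed and is not a misprint in the totals.

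**4. The sock-change rows.** The printed p-values correspond to 3 degrees of freedom. Table 6 shows three categories (2 df), and the questionnaire item ("How often do you change your socks") also offers three answers. If the every-two-days row (bacterial: 1 No, 4 Yes) is split into 1/3 and 0/1, the result is χ² = 4.085 on 3 df, p = 0.252. The corresponding fungal split gives 2.151, p = 0.542. Both agree with Table 7. The split is my inference. It suggests that four categories were tested and three displayed, not that the statistics were miscalculated.

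**5. Sensitivity on the printed counts.** Exact p-values (fungal, bacterial) are: foot washing 0.701, 0.693; flip-flops 0.628, 0.064; footwear 1.000, 0.574; sock type 0.334, 0.741; sock change on the three displayed rows 0.793, 0.158. All exceed 0.05. Flip-flops by bacterial infection depends on the method: 0.103 with continuity correction, 0.064 by Fisher's exact test, 0.045 uncorrected. Nine of the ten tables have an expected count below 5. The smallest is 2 × 8 / 49 = 0.33, and only footwear by bacterial infection is adequate, at 22 × 20 / 49 = 8.98.

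**6. What could the corrected result be?** The cross-tabulation on 13/28 is not given. As an assumption, keep every printed positive, hold the row totals fixed and add the missing 5 or 8. Fisher p then ranges as follows:

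| Comparison | Range of p |
|---|---|
| Flip-flops by bacterial | 0.003 to 1.0 |
| Flip-flops by fungal | 0.0005 to 1.0 |
| Footwear by bacterial | 0.003 to 1.0 |
| Footwear by fungal | 0.054 to 1.0 |

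These are bounds over possible placements, not probabilities.

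**The case against.** The strongest objection is about weight. The affected statement is a secondary association and not the comparison of the two concentrations. Exact tests on the printed counts leave it non-significant. The extremes in the last table need lopsided placements: p = 0.0005 requires all 5 missing fungal cases to fall among the 7 fungal-negative participants who did not use flip-flops. If the missing cases fell at random among the printed negatives, the chance of Fisher p below 0.05 would be about 26% for flip-flops by bacterial, 3% for flip-flops by fungal and 0.3% for footwear by bacterial infection. The ranges also presume that 13/28 is right, which the report does not establish. All of this stands, and it is why the result should be called undetermined and not fragile or reversed.

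A second defence is that Table 6 refers to another visit or definition. None is stated. A late visit also fits poorly, since the efficacy section reports that every fungal infection had resolved by day 30, whereas Table 6 shows 8 fungal positives. If another definition was used, stating it is part of the remedy.

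The sock-change categories and the choice of exact tests are side issues. They belong in the same re-tabulation but do not support the main point.

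**Conclusion.** The concern holds, and the text is wrong as written. The two sets of counts cannot both describe infection in the same 49 participants under the one stated rule. The gap is 5 fungal and 8 bacterial positives, and at least 4 of the 32 infected (4/32 = 12.5%) appear in neither column of Table 6.

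This part rests only on addition of printed figures. The report does not show which source is in error: the total of 32 appears in several places, but the 4/19/9 split appears only in the diagnostic text and Table 3.

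The no-relationship statement is therefore unsupported for now. Whether it would change cannot be determined from the report. No error is shown in Tables 4 and 5; which counts they used is a question for the authors.

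**What to change.** 1. Rebuild the infection counts from participant-level diagnoses, state the visit and definition used, and correct whichever of the diagnostic text, Table 3 or Table 6 is wrong.
2. Show in Table 6 the same sock-change categories that were tested.
3. Rerun Table 7 with Fisher's exact test for the 2×2 tables and the Fisher-Freeman-Halton test for the larger ones, then restate the hygiene conclusion from the result.
4. Add the number of infected participants per treatment group to Tables 4 and 5.

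The cost is one re-tabulation of existing data, ten small tests and a column of numbers in two tables.

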Scans and measurements were performed in a temperature-controlled room (20-24°C) and participants aired their bare feet for 10 minutes before starting the procedures, to normalize the temperature. In the first session they were weighed and measured (SECA 701, Vogel & Halke Hamburg, Germany), calculating the BMI(2). After normalizing the temperature, the physical examination was carried out, samples were taken, and data were obtained.

The Corneometer CM 825® (Electronic Courage-Khazaka, Cologne, Germany) with a measuring surface of 49 mm, a frequency of 0.9–1.2 MHz and an accuracy of $\pm 3\%$, was used to assess the superficial hydration of the skin (3). Five reference points were measured, both at the dorsal level and at the plantar level (Figure 2), obtaining three measurements from each point to later calculate the average hydration of each location analyzed.

[figure not shown]

Figure 2. Location of the 5 reference points on the feet for assessment of superficial hydration. (A) Dorsum of the foot: (1) dorso-distal point, above the central metatarsal heads. (B) Sole of the foot: (2) interdigital-plantar point, between 3rd and 4th digital space, (3) central point of the internal arch, (4) central point of the external arch, and (5) central point of the calcaneus.

Regarding the diagnosis of possible infections present in the feet, the following tests were performed:

- Wood's Light Examination

The feet of the participants were examined with a Wood L1004® lamp (Weelco, Barcelona, Spain) at maximum power (41) and at a distance of 10-15 cm from the surface to be examined. Long-wave ultraviolet radiation allows visual observation of the fluorescence emitted by *Pseudomonas aeruginosa*, *Microsporum audouinii*, *Microsporum canis*, *C. minutissimum*, *T. schoenleinii*,(4) among

others, whose color varies depending on the pathogen. The areas that fluoresced were recorded along with the color of the fluorescence in each review conducted from the beginning of the study to the day of its completion.

- Potassium hydroxide (KOH) test and mycological culture

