Statistical analysis was performed using the statistical analysis program IBM-SPSS Statistics for Windows version 25 (IBM Corp. Armonk, NY, USA). Some figures have been obtained using the Python programming language, using the Seaborn library (Waskom, M. L., (2021). Seaborn: statistical data visualization. *Journal of Open-Source Software*, 6(60), 3021, <https://doi.org/10.21105/joss.03021>).

Normality was assessed using the Shapiro-Wilk test. To evaluate the influence of different variables on infection remission, a Cox regression model was used, and survival curves of significant factors were plotted. To compare the efficacy of different EC concentrations, survival curves were compared using the Log-rank test. The Mann-Whitney U test was used to assess hydration averages according to sex. To check if there were improvements in hydration due to the use of the cream with different concentrations of EC (T1 and T2) compared to the control group (T0), hydration levels were compared using Kruskal-Wallis tests, using the Mann-Whitney U test with correction of p-values by the Bonferroni method for multiple comparisons.

In all statistical tests, significance was considered when p-value<0.05 and high significance when p-value<0.01.

2. Results

Analysis of the Elemental Composition of Commercial S. S.

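### Table 4's mean fungal remission times (11.61 and 14.00 days) precede the first review on day 15, remission is neither defined nor dated, and a log-rank p of 0.611 does not show similar efficacy

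*Combined protocol and SAP*

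**What the plan says.** **Schedule.** Under *Randomization, masking, and experimental design*, clinical evaluation after baseline was "on days 15, 30, 45 and 60 of treatment, except for cultures, both mycological and bacterial, which were performed at baseline, at 30 days". The last cultures were taken on day 60.

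**Diagnosis.** Under *Exploration, sampling, and diagnostic tests*, the rule for fungal infection is: "Participants with infection were considered to be those who had positive results in both tests, excluding cases in which only one test was positive". The two tests are KOH microscopy and culture. Of Wood's light the document says: "The areas that fluoresced were recorded along with the color of the fluorescence in each review conducted from the beginning of the study". It is the only infection examination stated to have been recorded at every review. There is no matching rule for remission, for the date given to it, or for censoring.

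**Planned test.** *Variables and statistical analysis* says: "To compare the efficacy of different EC concentrations, survival curves were compared using the Log-rank test". No equivalence margin is set.

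**Results.** *Efficacy of treatments* says "100% of fungal infections resolved within 30 days with both treatments" and gives the means: "the mean time to achieve remission in the T1 group (1%) was 11.61 days, compared to 14.00 days in the T2 group". Table 4 adds standard errors of 2.68 and 4.04, and 95% CIs of 6.36 to 16.86 and 6.09 to 21.91. From p = 0.611 the text concludes: "Therefore, both concentrations have similar efficacy in terms of the time required to achieve remission of infection".

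**Case counts.** *Test results for microbiological diagnostics* reports that, of 32 infected participants, "4 (12.5%) had fungal infection, 19 (59.4%) showed bacterial infection, and 9 (28.1%) had mixed fungal and bacterial infections simultaneously". Table 6 has 8 fungal and 20 bacterial infections among 49 participants and states no time point.

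**The concern.** Both reported means are earlier than any scheduled assessment after baseline. A reader would take 12 to 14 days as the clearance time for fungal infection, although no review or culture was made in that period. The fungal comparison of 1% with 0.5% rests on Table 4 and its log-rank test, so if the times are not remission times in infected participants, that comparison has no usable support.

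The statement that the two concentrations work similarly is a separate error of inference. It treats failure to find a difference as evidence that there is none.

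The problem reaches beyond Table 4. The bacterial remission times in Table 5 and the Cox models in Tables 8 and 9 rest on the same undefined endpoint. That includes the only significant factor in those models, sex in Table 9 (hazard ratio 4.11, p = 0.028).

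**Working it through.** **1. Reproduce the printed intervals** (mean ± 1.96 × SE, Table 4).
- T1: 11.61 ± 1.96 × 2.68 = 6.36 to 16.86 (printed 6.36 to 16.86).
- T2: 14.00 ± 1.96 × 4.04 = 6.08 to 21.92 (printed 6.09 to 21.91; rounding of the SE).

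Each row is internally consistent, so a typing slip in a mean is unlikely.

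**2. Earliest possible mean.** With remission dated at the visit where it is first seen, the smallest time for a participant infected at baseline is 15 days by review, or 30 days if a negative culture is needed. A mean cannot be below its smallest value. The printed means are 3.39 days (15 − 11.61) and 1.00 day (15 − 14.00) under the lower of these limits.

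**3. Share of times that must fall before day 15.** If a share x falls before day 15, the mean is at least 15(1 − x), so x ≥ 1 − mean/15.
- T1: 1 − 11.61/15 = 22.6%.
- T2: 1 − 14.00/15 = 6.7%.

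If the early times are all day 0 and all other remissions are dated day 30, the shares are 1 − 11.61/30 = 61.3% and 1 − 14.00/30 = 53.3%.

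**4. Could another dating rule explain it?** Midpoints of the first two review intervals are days 7.5 and 22.5. The share needed in the second interval is (11.61 − 7.5)/15 = 27% in T1 and (14.00 − 7.5)/15 = 43% in T2, so means below 15 are possible in principle. A search of patterns using these two dates, with or without censoring and with all remaining records remitting at the second date, found no match to either printed mean up to 32 (T1) and 18 (T2) records. If remission needs culture, the first midpoint is (0 + 30)/2 = 15 days, so the lower limit is still 15.

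**5. What does reproduce Table 4.** A search of remissions dated day 0, 15 or 30, with or without censoring, found no match within the stated arm sizes (25 and 12). Allowing up to 32 and 18 records, every match had 31 T1 records with 19 remissions at day 0, and 15 T2 records with 8 at day 0, with all other remissions at day 30.
- Means (area under the curve): 30 × 12/31 = 11.61 and 30 × 7/15 = 14.00.
- SE = mean × √[d₀/(n(n − d₀)) × m/(m − 1)], where d₀ is the number remitting at day 0 and m the number of events. T1 with m = 25: 11.613 × √[19/(31 × 12) × 25/24] = 2.68. T2 with m = 12: 14 × √[8/(15 × 7) × 12/11] = 4.04. In T1 any m from 23 to 26 also rounds to 2.68; in T2 only m = 12 fits.
- Log-rank: at day 30 everyone still at risk remits, so only day 0 contributes. Expected T1 events are 27 × 31/46 = 18.20. The variance is 27 × (31/46) × (15/46) × (19/45) = 2.505. χ² = (19 − 18.196)²/2.505 = 0.258, so p = 0.611, as printed.

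**6. Case counts.** Diagnostic results: fungal 4 + 9 = 13, bacterial 19 + 9 = 28. Table 6: 8 and 20. The reconstruction in step 5 uses 31 + 15 = 46 records, against 37 participants in T1 and T2 together.

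**7. What p = 0.611 can support.** At face value the difference is 14.00 − 11.61 = 2.39 days, SE √(2.68² + 4.04²) = 4.85, 95% CI −7.1 to 11.9 days. This is illustrative only, since the SEs are themselves in doubt.

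A second view does not use them. The detectable hazard ratio at 80% power is exp[(1.96 + 0.84)/√(D·p(1 − p))], taking two-sided 5% and a 25:12 split as assumptions. With D = 13 events it is about 5.3, and power for a hazard ratio of 2 is about 22%. With D = 8 it is about 8.3, with power about 15%.

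**The case against.** The strongest reply is that the 15-day limit depends on dating remission at the visit, and the document states no dating rule. That stands. A reader might infer that means below 15 days are impossible under any rule; the documents do not support that. Figure 4, which may show the dates of the steps, is not available here. What remains is that no rule is stated that would give these times, and the simple midpoint patterns tried do not reproduce them.

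A reader might also infer from step 5 that uninfected participants were certainly counted as remitted on day 0. That is not shown. The reconstruction needs more records than there were treated participants, and its T1 event count is not unique. The exact agreement with two means, two SEs and a p-value is a good reason to check the dataset, but it is not proof.

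It is fair to add that the number analysed is not given. The counts imply at most 13 participants with fungal infection, but this cannot be read as the n of the log-rank test. Nor do the blank medians in Table 4 add evidence: the document also prints a dash in Table 6 where the row and column totals show a zero.

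For the bacterial result, the text does say that the difference was not significant (p = 0.130) in the same sentence that calls T2 better. One might conclude that only the wording there needs correction. The undefined remission date and the 28 v 20 conflict apply equally to Table 5, so that narrower reading fails. Because Table 6 states no time point, the conflict calls for reconciliation and does not show which count is wrong.

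**Conclusion.** The point holds, on the condition that remission is dated at the visit where it is first seen. Under that condition Table 4's means of 11.61 and 14.00 days conflict with a minimum of 15 days by review, or 30 by culture. Without it, the means depend on a rule that the document does not give. In either case Table 4 and its log-rank test do not support a time to fungal remission.

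The conclusion of similar efficacy fails independently of the dating question. No margin was set, and with at most 13 fungal cases only a very large difference would have been likely to show. This is not evidence that the concentrations differ, nor that the cream fails to clear infection; the comparison is inconclusive.

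Table 5 and the Cox models in Tables 8 and 9 share the undated endpoint and the unresolved case counts. They need the same check, but nothing here shows that their figures are wrong.

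**What to change.** 1. State which tests establish remission and how it is dated. Check the dataset for event times before day 15, and for participants without the infection entered as remitted on day 0.
2. Reconcile the fungal (13 v 8) and bacterial (28 v 20) counts between the diagnostic results and Table 6, and state the time point of Table 6.
3. Rerun the fungal and bacterial efficacy analyses, including the Cox models, only in participants with that infection at baseline, one record each, and give cases and events per arm.
4. Replace Table 4 with the proportion cleared at day 30 and at day 60 by arm, with exact CIs and a CI for the difference. Keep a time-to-event comparison only if valid remission dates vary between participants. If every case is dated at the day-30 culture, such a comparison carries no information.
5. Label the Table 5 means as restricted to 60 days, since fewer than half of T1 had remitted by then.
6. Replace the claims of similar fungal efficacy and of a better bacterial result in T2 with a statement that no difference was detected and the comparison is inconclusive.

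The cost is a small reanalysis of existing data and revised text. The results will look less precise, and the fungal time comparison may have to be withdrawn.
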